5.2.1.1.1 Dose Limiting Toxicity Criteria

The same DLT criteria will be utilized for study Part A and Part B. All toxicities will be graded using CTCAE v 4.03. The DLT window of observation will begin at the administration of the initial dose of ADXS31-142 and end 1 week following the second dose of ADXS31-142. The occurrence of any of the following toxicities will be considered a DLT, if judged by the investigator to be possibly, probably or definitely related to study treatment administration. Treatment modifications for DLT are shown in Table 8 and Table 9.

General:

1. Prolonged delay (>2 weeks) in initiating the second dose due to treatment-related toxicity
2. Missing the second dose of ADXS31-142 or pembrolizumab (MK-3475) as a result of AE(s) during the first cycle.

Hematologic:

1. Grade 4 hematologic toxicity.
2. Febrile neutropenia, defined as absolute neutrophil count (ANC) $< 1000/\text{mm}^3$ with a single temperature of >38.3 degrees C (101 degrees F) or a sustained temperature of ≥ 38 degrees C (100.4 degrees F) for more than 1 hour.
3. Grade 3 thrombocytopenia lasting >72 hours.
4. Grade 4 thrombocytopenia.

Non-Hematologic:

1. \geq Grade 3 non-hematologic toxicity, (excluding nausea, vomiting and/or diarrhea lasting <3 days and reversible with medical intervention).
2. Grade 3 non-hematologic laboratory value that does not downgrade to Grade 2 within 3 days after onset of the event despite optimal medical management (excluding transient Grade 3 laboratory value abnormalities reversible within 5 days and without medical intervention).
3. Listeremia: positive blood culture(s) along with persistent (for 72 hours post dose) symptoms consistent with listeremia (e.g., fever and muscle aches, often preceded by diarrhea or other gastrointestinal symptoms).
4. \geq Grade 3 flu-like or cytokine release symptoms that persist for >24 hours after ADXS31-142 administration despite symptomatic treatment (Refer to Section 7.2.3.2).

Subjects who experience a DLT at Dose Level -1 of 0.5×10^9 will be discontinued from study treatment. However, subjects who experience a DLT at DL 1 of 1×10^9 may be eligible to receive ADXS31-142 at a lower dose level for subsequent doses and cycles following discussion and agreement between the Investigator and Sponsor.

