5.2.1.2 Treatment Delays and Modifications

5.2.1.2.1 Pembrolizumab (MK-3475)

Adverse events (both non-serious and serious) associated with pembrolizumab (MK-3475) exposure may represent an immunologic etiology. These AEs may occur shortly after the first dose or several months after the last dose of treatment. Pembrolizumab (MK-3475) must be withheld for drug-related toxicities and severe or life-threatening AEs as per [Table 8](#) below.

Table 8 Dose Modification Guidelines for Drug-Related Adverse Events with Pembrolizumab (MK-3475)

Toxicity	Hold Treatment For Grade	Timing for Restarting Treatment	Discontinue Subject
Diarrhea/Colitis	2-3	Toxicity resolves to Grade 0-1.	Toxicity does not resolve within 12 weeks of last dose or inability to reduce corticosteroid to 10 mg or less of prednisone or equivalent per day within 12 weeks.
	4	Permanently discontinue	Permanently discontinue
Hypophysitis	2-4	Toxicity resolves to Grade 0-1. Therapy with pembrolizumab (MK-3475) can be continued while endocrine replacement therapy is instituted.	Toxicity does not resolve within 12 weeks of last dose or inability to reduce corticosteroid to 10 mg or less of prednisone or equivalent per day within 12 weeks.
AST, ALT, or Increased Bilirubin	2	Toxicity resolves to Grade 0-1	Toxicity does not resolve within 12 weeks of last dose.
	3-4	Permanently discontinue (see exception below) ¹	Permanently discontinue
Type 1 diabetes mellitus (T1DM) (if new onset) or Hyperglycemia	T1DM or 3-4	Hold pembrolizumab (MK3475) for new onset Type 1 diabetes mellitus or Grade 3-4 hyperglycemia associated with evidence of beta cell failure	Resume pembrolizumab (MK-3475) when subjects are clinically and metabolically stable.
Hyperthyroidism	3	Toxicity resolves to Grade 0-1	Toxicity does not resolve within 12 weeks of last dose or inability to reduce corticosteroid to 10 mg or less of prednisone or equivalent per day within 12 weeks.
	4	Permanently discontinue	Permanently discontinue
Hypothyroidism	1-4	Therapy with pembrolizumab (MK-3475) can be continued while thyroid replacement therapy is instituted	Therapy with pembrolizumab (MK-3475) can be continued while thyroid replacement therapy is instituted.
Infusion Reaction	3-4	Permanently discontinue	Permanently discontinue
Pneumonitis	2	Toxicity resolves to Grade 0-1	Toxicity does not resolve within 12 weeks of last dose or inability to reduce corticosteroid to 10 mg or less of prednisone or equivalent per day within 12 weeks.

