5.2.1.2.2 ADXS31-142

The most likely anticipated AEs associated with ADXS31-142 are comprised primarily of individual flu-like symptoms (e.g., fatigue, lethargy and low grade fever) or cytokine release symptoms (e.g., constitutional symptoms such as fever, chills, rigors, headache, nausea, vomiting, tachycardia, shortness of breath, hypotension, and rash). These symptoms usually present within 2-4 hours after the completion of infusion and are often mild to moderate and transient in nature or respond quickly to symptomatic treatment. In rare instances, they may last up to 24 hours. No cumulative or delayed toxicity has been observed.

Less likely AE's include increase heart rate, low blood pressure, muscle aches, headaches, allergic reaction, changes in blood chemistry, changes in blood counts, and short term changes in liver function.

Rare but serious AEs include high fever, difficulty breathing and hypotension.

██████████ ADXS31-142 has a tropism for the liver. Transient asymptomatic elevations of ALT and alkaline phosphatase were observed after dosing with ADXS11-001 in the Phase 1 trial without prophylactic medication administration. For that reason, subjects with significant liver disease are excluded, and particular attention is to be paid to hepatic abnormalities.

The dose of ADXS31-142 will not be modified (e.g., reduced or increased) unless if it is determined that the toxicities are clearly attributed to ADXS31-142 or the combination, the treatment modification guidelines for drug-related AEs in [Table 9](#) shown below are to be followed.

Table 9 Treatment Delay/Discontinuation Guidelines for Drug-Related Adverse Events-ADXS31-142

Toxicity	Grade	Hold treatment	Timing for restarting treatment	Discontinue treatment
Hematologic	1-3	No	N/A	N/A
	4	Yes	Toxicity resolves to ≤Grade 1 or baseline	Toxicity does not resolve to ≤Grade 1 or baseline within 12 weeks
Non-hematologic, excluding cytokine release symptoms and DLTs	1	No	N/A	N/A
	2-3	Yes	Toxicity resolves to ≤Grade 1	Toxicity not resolved to ≤Grade 1 within 12 weeks of last infusion ^a
	4	N/A	Permanently discontinue treatment	Permanently discontinue treatment

^a With Investigator and Sponsor agreement, subjects with a non-heme AE (e.g., alopecia, neuropathy) still at grade 2 after 12 weeks, may continue treatment if only asymptomatic and controlled.

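### Non-hematologic DLT criterion 1 overrides the duration limits in criteria 2 and 4, so brief Grade 3 laboratory and cytokine-release events count as DLTs if the text is read literally (minor; effect size unknown)

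*Combined protocol and SAP*

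**What the plan says.** Section 5.2.1.1.1 applies the same DLT criteria to Parts A and B and joins them by OR: "The occurrence of any of the following toxicities will be considered a DLT", provided the investigator judges the event possibly, probably or definitely related. The window opens at the first ADXS31-142 dose and closes at the "end 1 week following the second dose of ADXS31-142".

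Three non-hematologic criteria bear on this point:

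- **Criterion 1** counts Grade 3 or higher non-hematologic toxicity, "excluding nausea, vomiting and/or diarrhea lasting <3 days and reversible with medical intervention".
- **Criterion 2** counts a Grade 3 non-hematologic laboratory value that "does not downgrade to Grade 2 within 3 days after onset of the event despite optimal medical management". It then exempts transient Grade 3 values that reverse within 5 days without intervention.
- **Criterion 4** counts Grade 3 or higher "flu-like or cytokine release symptoms that persist for >24 hours after ADXS31-142 administration despite symptomatic treatment".

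General criterion 2 separately makes a DLT of "Missing the second dose of ADXS31-142 or pembrolizumab (MK-3475) as a result of AE(s) during the first cycle". A subject with a DLT at Dose Level -1 is discontinued. A subject with a DLT at 1x10^9 cfu may continue at a lower dose by agreement.

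Table 9 (Section 5.2.1.2.2) has a row headed "Non-hematologic, excluding cytokine release symptoms and DLTs". Table 10 (Section 5.6.1.8) responds to Grade 3 cytokine-release symptoms other than hypotension by lengthening later infusions to 2 hours and considering more prophylaxis. Section 7.2 includes abnormal laboratory findings among adverse events.

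**The concern.** Criteria 2 and 4 say that certain Grade 3 events count only if they last. Criterion 1 counts the same events at onset. Because the list is disjunctive, criterion 1 prevails, and the persistence limits and the transient-value exclusion do nothing. Two careful readers could report different DLT counts for the same subjects.

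Part A is complete (Section 5.2.1.1.2), so what remains at stake is Part B. Under the modified 3+3 rule of Section 5.2.1.1.3, one reclassified subject can turn 2/6 (dose accepted) into 3/6 (de-escalate). It can also stop a first cohort at 2/3 where 1/3 would have opened a second cohort. At Dose Level -1 the overlap also affects the individual subject: a brief, related Grade 3 rigor or fever is a DLT that ends treatment under Section 5.2.1.1.1, while Table 10 says to extend the infusion and carry on.

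**Working it through.** **Step 1: which events are double-covered.**

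| Event (related, inside the window) | Criterion 1 | Specific criterion | Literal result |
|---|---|---|---|
| Grade 3 laboratory value, persistent | DLT | DLT (2) | DLT |
| Grade 3 laboratory value, transient | DLT | not a DLT (2) | DLT |
| Grade 3 flu-like or cytokine-release symptom, non-GI, >24 h | DLT | DLT (4) | DLT |
| The same, 24 h or less | DLT | not a DLT (4) | DLT |
| Grade 3 cytokine-release nausea or vomiting, >24 h but <3 days and reversible | exempt | DLT (4) | DLT |

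Criterion 2 never changes the result. Criterion 4 changes it only in the last row. The disputed events are those in rows 2 and 4.

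**Step 2: how much of the laboratory half is live in Part B.** The Section 6.2 flow chart schedules serum chemistry at Weeks 1, 4, 7 and 10, and Section 7.1.3.1 places the samples within 3 days before dosing. The second ADXS31-142 dose is at Week 4 and the window closes a week later. The Week 4 pre-dose sample is therefore the only scheduled on-treatment chemistry in the window. For related Grade 3-4 AST, ALT or bilirubin, Table 8 says "Permanently discontinue (see exception below"; the exception covers subjects with liver metastasis who start at Grade 2 AST or ALT. Such a rise before the second pembrolizumab dose would normally make the subject miss that dose, which is already a DLT under General criterion 2. The laboratory half is real but narrow.

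**Step 3: direction and sensitivity of the Part B decision.** The plan states no operating characteristics for the 3+3, so there is no figure to reproduce. Let X1 and X2 be the DLT counts in the first and second cohorts of 3, each Bin(3, p). From Section 5.2.1.1.3:

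P(de-escalate) = P(X1>=2) + P(X1=1)·P(X2>=2) + P(X1=0)·P(X2=3)

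This increases with p, so extra DLTs can only push toward the lower dose. Let q be the chance per subject of an event that only the literal reading counts, taken as independent of other DLTs. Then p* = 1 - (1-p)(1-q).

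Worked case at p = 0.25, the DLT target stated for Part A in Table 5, used only as a reference:

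- q = 0: 0.15625 + 0.421875×0.15625 + 0.421875×0.015625 = 0.2288.
- q = 0.01: p* = 1 - 0.75×0.99 = 0.2575, giving 0.16477 + 0.42588×0.16477 + 0.40935×0.01707 = 0.2419.

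The probability rises from 22.9% to 24.2%, or 1.3 points.

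Base rates of 5-30% and all values of q are assumptions. Each q column shows the resulting probability and, in brackets, the rise in points:

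| Base p | q = 0 | q = 1% | q = 2% | q = 4% | q = 10% |
|---|---|---|---|---|---|
| 5% | 0.8% | 1.2% (0.4) | 1.6% (0.8) | 2.7% (1.9) | 7.7% (6.9) |
| 10% | 3.6% | 4.3% (0.7) | 5.0% (1.5) | 6.7% (3.2) | 13.4% (9.8) |
| 20% | 14.8% | 16.0% (1.2) | 17.2% (2.4) | 19.8% (5.0) | 28.3% (13.5) |
| 25% | 22.9% | 24.2% (1.3) | 25.5% (2.7) | 28.3% (5.4) | 36.9% (14.0) |
| 30% | 32.1% | 33.4% (1.3) | 34.8% (2.7) | 37.5% (5.4) | 45.8% (13.8) |

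Because the literal reading only adds DLTs, each rise is also the probability that the two readings lead to different decisions at the first Part B level.

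**The case against.** The strongest reply is that a sensible reader lets the specific criterion govern over the general one, and that overlap is this list's style: hematologic criterion 4 repeats part of hematologic criterion 1. The second part does not help, because that repetition gives the same answer twice, whereas criteria 2 and 4 set different thresholds. The first part may well describe the intent, but the text says any listed toxicity suffices and states no precedence.

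A reader might infer from Tables 9 and 10 that the protocol proves brief cytokine-release events are not DLTs. It does not. Table 9's row heading concerns holding and restarting treatment, and excludes DLTs alongside cytokine-release symptoms. Table 10's continued dosing is compatible with a DLT at 1x10^9 cfu, since such a subject may go on at a lower dose. The tables suggest intent. The direct conflict is only at Dose Level -1.

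The safeguards against a bad decision stand. Any AE of Grade 3 or higher is an event of clinical interest reportable within 24 hours (Section 7.2.3.2). De-escalation may rest on interim safety review as well as DLTs (Section 5.2.1.1.3), and the Sponsor decides only after discussion with investigators (Section 5.2.1.1). Inconsistent counts would probably be noticed. The safeguards do not say which count is right, and settling that after the events are known is what a prespecified definition should avoid.

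**Conclusion.** The criteria contradict each other as written. This is a minor defect. The literal reading errs toward the lower dose, so it does not expose subjects to a more toxic one. The cost is a possible unneeded de-escalation to 0.5x10^9 cfu, or discontinuation of a subject at Dose Level -1 whom Table 10 would keep on treatment.

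The size is unknown. The documents give no rate for transient Grade 3 laboratory values or for Grade 3 flu-like or cytokine-release symptoms of 24 hours or less, and none for the combination. Section 4.2.2.1 describes class symptoms as almost all low grade, which points to a small effect but does not establish one. At a hypothetical added rate of 10% the rise would be 7 to 14 points.

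Two stronger readings are tempting. One takes the roughly 1% Grade 3-4 hypotension figure in Section 5.6.1.8 as the added rate and concludes that the effect is about a point. That figure covers one symptom, includes Grade 4 events that remain DLTs under either reading, and says nothing about duration, so it does not estimate the disputed events. The other says that moving from 1/3 to 2/3 reverses an accepted dose. It does not: 1/3 only opens a second cohort, and that cohort could still have failed.

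**What to change.** Add to criterion 1: *and excluding Grade 3 non-hematologic laboratory values and Grade 3 flu-like or cytokine-release symptoms, which are assessed under criteria 2 and 4 respectively*. Keep all Grade 4 events as DLTs under criterion 1 and leave the General criteria unchanged. Whether Grade 3 hypotension or dyspnea should remain a DLT at any duration is an optional clinical choice for the sponsor; the present criterion 4 does not single either out.

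The clause alone leaves criterion 2 with both a 3-day and a 5-day limit. Replace them with one resolution limit, and require a repeat test within it whenever a Grade 3 value is found. The scheduled draws cannot show whether a Week 4 abnormality resolved in a few days.

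Apply the change prospectively to Part B. For subjects already evaluated, tabulate DLTs under both readings, and do not reverse a conservative decision already made.

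The cost is the amended wording, an occasional repeat blood test, and one extra tabulation for 3 to 6 subjects per dose level. The downside is a DLT definition slightly less conservative than the literal text for brief Grade 3 events.

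### Non-hematologic DLT criterion 1 has no grade cap on its short-diarrhea exclusion, so a brief, reversible Grade 4 diarrhea after dose 2 is not clearly counted in the Part B 3+3

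*Combined protocol and SAP*

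**What the plan says.** Section 5.2.1.1.1 gives one DLT list for both parts of the trial. The observation window opens with the first ADXS31-142 dose and is to "end 1 week following the second dose of ADXS31-142". The items that matter here are:

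- **Non-hematologic 1:** related toxicity of Grade 3 or higher, "excluding nausea, vomiting and/or diarrhea lasting <3 days and reversible with medical intervention".
- **Non-hematologic 2:** persistent Grade 3 laboratory values, "excluding transient Grade 3 laboratory value abnormalities reversible within 5 days and without medical intervention".
- **Non-hematologic 4:** Grade 3 or higher "flu-like or cytokine release symptoms that persist for >24 hours after ADXS31-142 administration despite symptomatic treatment".
- **Hematologic 3 and 4:** "Grade 3 thrombocytopenia lasting >72 hours" is a DLT, and Grade 4 thrombocytopenia is a DLT whatever its duration.
- **General 2:** "Missing the second dose of ADXS31-142 or pembrolizumab (MK-3475) as a result of AE(s) during the first cycle".

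The section adds that "Treatment modifications for DLT are shown in Table 8 and Table 9", and that subjects with a DLT at Dose Level 1 (DL 1) "may be eligible to receive ADXS31-142 at a lower dose level for subsequent doses and cycles" if the Investigator and Sponsor agree. A DLT at DL -1 ends study treatment.

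Table 8 (section 5.2.1.2.1) permanently stops pembrolizumab for Grade 4 diarrhea/colitis. Table 9 (section 5.2.1.2.2) permanently stops ADXS31-142 for Grade 4 non-hematologic toxicity, but only where toxicity is clearly attributed to ADXS31-142 or the combination, and that row leaves out cytokine release symptoms and DLTs. The Part B rule in section 5.2.1.1.3 accepts a dose at 2/6 DLTs or fewer, and de-escalates at 3/6 or more, or at 2/3 or 3/3 in the first cohort.

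**The concern.** Table 16 (section 7.2.4) defines Grade 4 as life-threatening with urgent intervention indicated. Urgent treatment can reverse such an event within 3 days, and it then fits the wording of the exclusion. The protocol regards the event as serious enough to end pembrolizumab for that subject, yet after dose 2 the dose-finding count need not register it.

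The count decides which dose goes into the expansion, and selecting that dose is part of the Part B primary objective. Leaving out one event can move a dose from de-escalate to accept. Whether the event counts also depends on which infusion it followed and not on how severe it was. The point concerns Part B only, because section 5.2.1.1.2 records Part A as completed.

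**Working it through.** The plan states no operating characteristic for this rule, so there is no figure to reproduce. The check has three parts.

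**1. Does another DLT item catch the event?** Take a related Grade 4 diarrhea in the week after dose 2 that reverses in under 3 days.

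| DLT item | Catches it? |
|---|---|
| General 1 and 2 | No. They concern delay or omission of the second dose, which has been given. |
| Hematologic 1 to 4 | No. They are blood-count items. |
| Non-hematologic 1 | Excluded by the parenthesis. |
| Non-hematologic 2 | No. Laboratory values only. |
| Non-hematologic 3 | Only with a positive blood culture and persistent symptoms. |
| Non-hematologic 4 | Not clearly. Diarrhea is not among the cytokine release symptoms in section 5.6.1.8, nor among the flu-like or cytokine release examples in section 5.2.1.2.2. Persistence beyond 24 hours is also needed. |

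Nausea and vomiting are listed cytokine release symptoms, so criterion 4 reaches them once they persist beyond 24 hours. Grade 4 vomiting that resolves within 24 hours falls in the same gap.

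After dose 1 the result differs. The Table 8 stop means the second pembrolizumab dose is missed because of an adverse event, and General criterion 2 makes the event a DLT.

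**2. Effect on the count, for a subject with no other DLT.**

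- 2 counted DLTs plus 1 such event among 6: 2/6 (accept) as written, 3/6 (de-escalate) if counted.
- 1 counted DLT plus 1 such event among the first 3: 1/3 (enroll 3 more) as written, 2/3 (de-escalate) if counted.

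**3. Effect on the chance of accepting DL 1.** With b(k) the Binomial(3, p) probability of k DLTs, the section 5.2.1.1.3 rule gives

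A(p) = b(0)·[1 − b(3)] + b(1)·[b(0) + b(1)].

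At p = 0.25, b(0) = b(1) = 0.421875 and b(3) = 0.015625, so A = 0.421875 × 0.984375 + 0.421875 × 0.84375 = 0.7712.

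Inputs that are assumptions:

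- The rate u of uncounted events is 0.1% to 1% of subjects. The documents give none. The roughly 1% in section 5.6.1.8 is for Grade 3-4 hypotension and is not used.
- The counted DLT rate c is 25%, borrowed from the Part A target in Table 5, with 15% and 35% as a range. Part B states no target.

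*No overlap with other DLTs (upper bound), true rate c + u:*

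| c | A as written | A, u = 0.1% | A, u = 1% | Fall, points |
|---|---|---|---|---|
| 15% | 91.74% | 91.63% | 90.57% | 0.11 to 1.17 |
| 25% | 77.12% | 76.95% | 75.36% | 0.17 to 1.76 |
| 35% | 58.15% | 57.95% | 56.16% | 0.20 to 1.99 |

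*Independent of other DLTs, c = 25%:* the true rate is 1 − 0.75 × (1 − u), which is 0.25075 or 0.2575. A is 76.99% or 75.81%, a fall of 0.13 to 1.32 points.

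*Chance of at least one such event in 6 subjects:* 1 − 0.999^6 = 0.6%, up to 1 − 0.99^6 = 5.9%.

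**The case against.** **The allowance may be deliberate.** The thrombocytopenia and laboratory allowances stop at Grade 3, which invites the inference that criterion 1 contradicts its own section. The documents do not support that. Criterion 4 has the same structure as criterion 1, with a duration limit and no upper grade. The two clinical-symptom items are limited by duration and the two blood or laboratory items by grade, which fits a deliberate allowance for short expected symptoms as well as it fits a slip. This objection stands. The case for a cap rests on the consequences of the wording and not on an internal contradiction.

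**The case is narrow.** A reader might infer that Grade 4 diarrhea in general escapes the count. It does not. The event must be short, reversible and in the single week after dose 2. An accompanying toxicity recorded at Grade 3 or higher, such as hypotension, dehydration or colitis, can count in its own right. The symptom lists are illustrative, so an investigator might apply criterion 4 to diarrhea lasting more than 24 hours. All of this stands, and it is why the conclusion says *not clearly* a DLT.

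**Other safeguards exist.** The event is not hidden. Any adverse event of Grade 3 or higher is an event of clinical interest reported within 24 hours (section 7.2.3.2). Interim safety review may prompt de-escalation, an intermediate dose is allowed (section 5.2.1.1.3), the Sponsor decides after discussion with Investigators (section 5.2.1.1), and section 5.11 allows termination on the severity of adverse reactions. These reduce the risk. They are judgments, however, and do not repair the counting rule.

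**The effect is small.** At an assumed 10% event rate the same formula gives a 19.0-point fall (77.12% to 58.15%), but nothing in the documents supports such a rate. Section 4.2.2.1 describes the flu-like and cytokine release symptoms of this class as nearly all low grade.

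**Conclusion.** The point holds in a limited form. As written, a related Grade 4 diarrhea in the week after dose 2 that reverses in under 3 days, with no other qualifying toxicity, is not clearly a DLT, while the same event after dose 1 is. Grade 4 vomiting that resolves within 24 hours is left out in the same way.

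Under the assumed 0.1% to 1% event rate and 25% counted DLT rate, the effect on accepting DL 1 is at most about 0.2 to 1.8 points. A life-threatening event is likely to overlap with other DLTs, so the real effect is probably smaller. This is a gap in the counting rule and not in safety detection. It is worth closing because the correction is small and the count drives the Part B dose decision.

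**What to change.** 1. **Cap the exclusion for Part B.** In the parenthesis of non-hematologic criterion 1, insert *Grade 3* before the word nausea. At the opening sentence of section 5.2.1.1.1, which applies one list to both parts, note that the cap applies to Part B from the amendment onward, since Part A is completed.

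2. **Keep the present treatment stop for this event.** The Table 9 non-hematologic row leaves out DLTs. Reclassification alone would therefore take the event out of the mandatory ADXS31-142 stop and open the optional lower dose at DL 1. Add to that row: *Grade 4 diarrhea that is a DLT remains subject to the Grade 4 permanent discontinuation in this row.* Add to the DL 1 lower-dose sentence: *except Grade 4 diarrhea for which Table 9 requires permanent discontinuation.* Placed there, the stop keeps its existing condition of clear attribution. DL -1 needs no edit.

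The Table 9 line should not be widened to all Grade 4 non-hematologic DLTs. That would remove the lower-dose option more broadly and draw in cytokine release events, which should stay under Table 10.

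The cost is a short amendment, DLT definitions that differ slightly between Parts A and B, and a slightly higher chance of de-escalation to DL -1.
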